Determining which patients, using age and arthritic burden as predictors, can benefit from labral repair is paramount for several reasons. Showing arthroscopic repair is of little or no benefit to a specific cohort can reduce the number of unnecessary surgeries performed, increase the use of conservative therapy (if validated) and reduce the interval between diagnosis and total hip replacement. Additionally, proving a benefit exists from arthroscopic repair in a certain subset of the population will substantiate the need for developing a treatment algorithm in older patients presenting with labral tears and some degree of pre-existing arthritis. Furthermore, conservative physical therapy may prove to be of equal or greater benefit than arthroscopic repair in select patients. If true, this study will be a landmark for providing the evidence needed to recommend conservative treatment as an efficacious alternative in addition to providing a foundation for future research on this topic.

II. SPECIFIC AIMS:

Specific Aim 1: To evaluate if physical therapy alone or arthroscopic labral repair and physical therapy is of greater benefit to patients presenting at age 40 with tears of the acetabular labrum.

Hypothesis 1.1: Physical therapy will result in a significant difference in mHHS scoring at 12 months when compared to baseline.

Hypothesis 1.2: Arthroscopic labral repair will result in a significant difference in mHHS scoring at 12 months when compared to baseline.

Hypothesis 1.3: Arthroscopic labral repair and physical therapy will be superior to physical therapy alone in improving function and alleviating symptoms at 12 months when compared to baseline, as judged by the mHHS.

Hypothesis 1.4: Hypotheses 1.1-1.3 will hold true at 24 months and beyond.

Hypothesis 1.5: Functional outcome scores collected at the completion of PT will not significantly differ from those collected at 12 and 24 months and beyond in the same group.

Specific Aim 2: To evaluate the effect of arthritic burden on short term outcomes following arthroscopic labral repair.

Hypothesis 2.1: In the surgical treatment group, subjects with arthroscopically proven severe osteoarthritis (Outerbridge grade 4) will do more poorly on validated outcome measures, specifically the mHHS, after arthroscopy than subjects with less severe osteoarthritis (Outerbridge grade ≤ 3).

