Our Primary Outcome is change in the modified Harris Hip Score at 12 months and 24 months. Secondary outcomes include changes in other validated outcomes measures patient satisfaction, and degree of improvement on physical exam. The influence of OA severity (Outerbridge scoring) and location of OA will also be analyzed to determine if they have an effect on the aforementioned outcome measures. Satisfaction will be assessed by an exit questionnaire (See section IV). In addition to gauging satisfaction, this questionnaire will ask subjects how they felt about their participation in the study. (See section IV)

Inclusion and Exclusion Criteria:

Inclusion criteria	Rationale
Age 40 or greater	Higher likelihood of undetectable OA on imaging
Orthopedic surgeon determines symptoms are consistent with a labral tear.	Required for treatment
Availability of hip radiographs and MRI	Needed to assess eligibility and comparison for specific aim 3
Willingness to undergo randomization and ability to understand and sign informed consent document	Ability to understand study and consent willingly

Exclusion criteria	Rationale
Unexpected pathology at the time of arthroscopy	Source of pain less likely to due dysfunction of the labrum and more likely due to aberrant extra-articular biology
Same site surgery	Complex anatomy
Contraindication to surgery or physical therapy	Cannot tolerate either treatment grouping
Alternate form of PT for greater than 6 weeks	Will negatively augment results. May affect recruitment.

Selection and enrollment:

We will enroll 122 consecutive subjects meeting the aforementioned criteria. Subjects will be randomized into conservative or surgical treatment arms. All potential subjects on the clinic schedule of the investigator will be pre-screened for eligibility based on age, clinical assessment, and previous medical history.

All eligible subjects will be approached at an outpatient clinic visit. Those who initially meet inclusion criteria will be introduced to the study and given a research consent form that they have the opportunity to take home and to review.

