The mean outcome scores of the mHHS in each treatment group at 12 months will be compared to baseline scores to assess for significant differences using paired sample t-test in SPSS 16 (SPSS, Chicago, IL). The mean outcomes scores of the mHHS between groups at 12 months will be compared using independent t-tests to assess for significant difference. We will use a Levene test to judge variance and proceed accordingly. If a statistically significant difference is detected during these analyses, we will calculate the effect size (ES) to determine how meaningful these results are outside of being statistically significant. The ES will be calculated by: [(mean mHHS score of surgical arm / mean mHHS of the conservative group) / standard deviation of the conservative group]. According to Cohen ⁵⁸, an ES <0.1 is trivial, ES of 0.1-0.3 is minimal, ES of 0.3-0.5, is moderate, and ES >0.5 is large. We will repeat the same analysis at 12 months.

Hypothesis 2.1, 2.2, and 2.3:

Diagnosis and treatment of the prearthritic and early arthritic hip has been an area of intense interest. However, our most conventional method of assessment (plain radiography) does not provide us with enough diagnostic sensitivity.⁴¹ Direct visualization on the articular surfaces in the hip is both sensitive and specific. Furthermore, emphasis is being placed on the location of arthritis as a prognostic indicator of good outcomes following hip arthroscopy. The value of arthroscopic techniques for primary

symptoms and/or prevention of OA secondary to labral tears remains unclear even though preliminary reports indicate there may be some benefit to repairing a torn labrum, even in cases of severe OA. Evaluation of arthritic change at the time of arthroscopy is important, particularly in subjects where there remains uncertainty about the efficacy of labral repair for those with articular or rim cartilage degeneration that the effects of those changes on long-term OA progression.⁵⁹

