Using the data from our retrospective review of outcomes following labral repair, a 10 point or greater difference on the mHHS as significant, and a single-tail independent t-test to evaluate the difference between means with 80% power and a 5% significance level, 35 subjects are needed to demonstrate a statistically significant difference between the average mHHS of the conservative group and surgical group. Testing of hypothesis 1.5 will be an intragroup analysis looking for a significant difference in outcome measures from the time of completion of PT (non-crossover) when compared to the same data to be collected at 12 months and 24 months. The purpose is to determine the short-term durability of the response to PT, if one is found.

70 study completers should provide us with the necessary data needed to substantiate or reject our hypothesis. There has been no prospective trial to date testing these hypotheses in the hip, but we expected a 7.3-10.3% dropout rate based on the results of a similar study in the knee. However, as of July 2018, we had 47 patients that had passed the 2-year follow-up mark, of which 5 patients were no longer in the study (combination of lost to follow-up and proceeding to total hip arthroplasty), and another 11 had yet to complete their 2-year surveys even with multiple attempts to contact them and encourage them to do so. With a yield of 31 patients out of 47, or 65.95%, we increased our sample size to 122.

Therefore, we estimate needing 122 subjects to achieve 70 study completers, in the appropriate proportion of 35 subjects per treatment arm. We enroll until reaching at least 35 subjects in each group.

The results of the MeTeOR trial in the knee show that we can expect a higher drop-out rate in the surgical group. As such, this cohort may be our limiting factor.^{40, 43, 61, 62}

Specific Aim 2. Hypotheses 2.1-2.3: *To evaluate the significance of arthritic burden on short term outcomes following arthroscopic labral repair.*

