1. The study staff will meet regularly with [name] to review study participants and the data that has been collected on them to date. If a subject becomes disqualified or must leave the study for safety concerns, [name] will personally inform them of the situation through the subjects preferred method of contact. [name] will be leading and administering the conservative arm of the study (subjects being treated non-surgically with physical therapy and subjects in the post-operative period receiving rehabilitative physical therapy). She will inform [name] of patient progress and any potential clinically significant events that may warrant further discussion and could ultimately result in the dismissal of a patient from the study.
 - a. As this is a prospective study comparing the gold standard of treatment (labral repair) to a potentially equivalent therapeutic modality, qualifying subjects will never be denied the option to undergo labral repair via hip arthroscopy. The treatment schema allows for subjects in the non-surgical arm (physical therapy alone) to cross over to the surgical treatment group at any time (following physical therapy) from initial enrollment if they wish to do so. Subjects who decide to crossover or are indicated to crossover through the non achievement of advancement criteria will have the PT discontinued at that time point but must wait for official crossover at 6 weeks after initial enrollment. Participants can always decide to leave the study if this is not what they want. The decision to cross over will in no way affect the quality of healthcare current or prior study participants receive. All of this will also be explained to them during the consent.
 - b. We will review all data continuously and should there be a obvious clinical detriment to specific treatment arm such as repeated poor outcomes or worsening function, further investigation will be initiated to determine if this is an isolated occurrence or if there is a significant trend which warrants cessation of study protocol and disenrollment of subjects.
 - i. Stopping rules include a clear difference in morbidity, as measured by interval physical exams and outcomes questionnaires, between treatment groups
 - ii. Any significant mortality possibly linked to study procedures will result in immediate suspension of the study protocol.

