2. A data safety monitoring board (DSMB) or data monitoring committee (DMC) is not required for the purposes of this study because large numbers of subjects will not be used in this investigation, there are no blinded treatment study groups, we are not using multiple clinical sites (all are within Partners network), we are not using high risk interventions (hip arthroscopy has been shown to be a safe option for managing intra-articular and periarthritis pathology of the hip;

physical therapy is low risk), we are not performing a controlled trial in which major morbidity or mortality are considered primary or secondary endpoints.

Adverse Events Reporting and Assessment:

Any protocol deviations and/or adverse events will be systematically documented and reported to the IRB. Adverse Event Reports and/or Case Report Forms will identify study participants by their initials and a unique study participant identifier.:.

Severity grading scale:

Mild: adverse event of little clinical significance

Moderate: adverse event between mild and severe - causing some limitation of usual activities

Severe: adverse event that results in death, is life-threatening, requires or prolongs hospitalization, causes persistent or significant disability/incapacity, represents a significant overdose or breach of protocol, results in congenital anomalies/birth defects or produces cancer, or in the opinion of the investigator, represents other significant hazards or potentially serious harm to the research subject or others.

Attribution scale:

Not related: clearly NOT related to the study

Possible: may be related to the study

Probable: likely related to the study

Definite: clearly related to the study

Unable to assess

Any serious or unexpected adverse events will be reported to the IRB within the required timeframe, using the appropriate forms. The principal investigator will provide an interim report of all adverse events to the IRB at the time of continuing review. Although this proposed project is perceived to be relatively low-risk, the study may be terminated if the frequency of serious or unexpected adverse events is higher than that anticipated. Once this determination is made, a memo will be sent to the IRB explaining the reasons for the determination. For suspended studies, an action plan will be devised which will outline what evidence and/or conditions will be required to terminate or re-initiate the study.

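### The between-arm mHHS test ignores the collected baseline, which can cost precision, and the 24-month repeat is written as 12 months

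*Combined protocol and SAP*

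**What the plan says.** Section V (Hypothesis 1.1-1.4) plans paired t-tests of 12-month against baseline mHHS within each arm. For the comparison of the arms it says: "The mean outcomes scores of the mHHS between groups at 12 months will be compared using independent t-tests to assess for significant difference". A Levene test is to guide the handling of unequal variances. The paragraph closes with "We will repeat the same analysis at 12 months".

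Three other places bear on this:

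- Section III, Study Overview: "Our Primary Outcome is change in the modified Harris Hip Score at 12 months and 24 months".
- Section II: "Hypothesis 1.4: Hypotheses 1.1-1.3 will hold true at 24 months and beyond".
- Section V, Power Analysis: the trial is sized on "a single-tail independent t-test to evaluate the difference between means with 80% power and a 5% significance level", with a 10-point difference and 35 completers per arm.

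No section adjusts the comparison of the arms for baseline. The linear regressions in Section V concern arthritis severity and joint-space narrowing, not treatment arm.

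**The concern.** Baseline mHHS is in hand for the within-arm tests, yet the comparison that answers the trial's question does not use it. If baseline and follow-up scores are correlated, part of the spread in 12-month scores is predictable from baseline. A test on raw means leaves that spread in the error term. The same patients would then give a wider confidence interval and less power than they could.

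The endpoint is also worded as change while the test uses the final score. A sponsor who aligned the two by switching to a plain change-score t-test could lose power.

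Separately, the closing sentence repeats an analysis that is already at 12 months. Read literally, the section contains no 24-month comparison of the arms, although 24 months is a named primary time point.

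**Working it through.** **Inputs from the Power Analysis.** Difference 10 points, one-sided 5%, power 80%, 35 per arm. The SD is not stated. No section gives the correlation r between baseline and 12-month mHHS, or k, the baseline SD divided by the 12-month SD. Values of r and k below are assumptions.

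**Step 1: the plan's figure.** Without an SD, the 35 per arm cannot be verified; it can only be solved backwards. With the noncentral t distribution on 68 degrees of freedom and noncentrality d·√(35/2), 80% power requires d = 0.600. So SD = 10/0.600 ≈ 16.7 points. The 80% for raw means therefore holds by construction.

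**Step 2: ANCOVA.** Adjustment multiplies the residual variance by 1 − r², so d becomes 0.600/√(1 − r²) on 67 degrees of freedom. Chance baseline imbalance multiplies the variance of the estimate by about 1 + 1/(2·35 − 4) = 1 + 1/66.

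| r (assumed) | Power, ANCOVA | Power, allowing for chance imbalance |
|---|---|---|
| 0 | 80.0% | 79.5% |
| 0.1 | 80.3% | 79.8% |
| 0.2 | 81.4% | 80.9% |
| 0.3 | 83.2% | 82.7% |
| 0.5 | 89.0% | 88.6% |
| 0.7 | 96.7% | 96.5% |

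With imbalance included, ANCOVA breaks even with raw means at r ≈ 0.12. It gains 1 point of power at r ≈ 0.21, 5 points at 0.39 and 10 points at 0.54.

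**Step 3: interval width.** For raw means the 95% half-width is 1.995 × 16.66 × √(2/35) ≈ 7.9 points. With ANCOVA, before the small imbalance factor, it is 7.6, 6.9 or 5.7 points at r = 0.3, 0.5 or 0.7.

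**Step 4: plain change score.** The variance is multiplied by 1 + k² − 2rk, so change beats raw means only if r exceeds k/2. At k = 1 its power is 68%, 80% or 94% at r = 0.3, 0.5 or 0.7. At k = 0.8 it is 75%, 86% or 96%, and at k = 1.2 it is 60%, 72% or 89%.

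**Step 5: simulation.** In 20,000 simulated trials of 35 per arm with k = 1 and r = 0.5, power was 80.0% for raw means, 79.7% for change and 88.4% for ANCOVA. The mean ANCOVA estimate was 10.0 points, the true difference.

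**Step 6: sidedness.** If the 35 per arm is read as a two-sided calculation, the implied SD is 14.7. ANCOVA power is then 83.6%, 89.9% or 97.5% at r = 0.3, 0.5 or 0.7, which is the same picture.

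**The time point.** The paragraph is headed Hypothesis 1.1-1.4, Hypothesis 1.4 concerns 24 months and beyond, and the primary outcome names 24 months. The second 12 months can only be a slip for 24.

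**The case against.** The strongest case against is that an independent t-test on follow-up means is a legitimate pre-specified analysis that agrees with the sample size calculation. The gain from ANCOVA rests on a correlation the documents do not give. Below about r = 0.12 there is a small loss, and nothing in the documents shows on which side the trial lies. All of that is true. It limits the claim to a possible gain in efficiency.

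Timing is a second objection. The plan reports that "as of July 2018, we had 47 patients that had passed the 2-year follow-up mark", that "there are no blinded treatment study groups", and that "We will review all data continuously and should there be a obvious clinical detriment to specific treatment arm" there will be further investigation. Replacing the primary test late could look data-driven. This stands as a real procedural cost. It can be limited but not removed.

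Third, saying that the omission causes no bias applies only to leaving out a covariate from an intact randomised comparison. Subjects with unexpected pathology at arthroscopy are removed after randomisation, and only 31 of 47 had usable 2-year data. In an assumed extreme case (r = 0.5, 61 per arm, about 35% missing, dropout depending on baseline in opposite directions by arm), the raw t-test averaged 14.8 and ANCOVA 9.9 against a true 10. That is a missing-data problem and a separate matter, but it does not favour the unadjusted test.

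Finally, ANCOVA would drop the Levene provision unless unequal variances are dealt with in another way. Robust standard errors do this.

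**Conclusion.** The point holds. The comparison of the arms omits a baseline that is already collected, and nothing elsewhere in the document supplies the adjustment. The consequence is lost precision of unknown size: nothing to speak of at r up to about 0.2, and roughly 3, 9 or 16 points of power at r = 0.3, 0.5 or 0.7. These figures assume an SD of about 16.7, back-solved from the plan, 35 completers per arm and complete data. The omission and the wording slip are certain from the text; the size of the gain is not.

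The planned test is neither invalid nor inconsistent with the sample size. This is an improvement that should be made. The repeated 12 months is editorial, but it needs correcting because the section otherwise lacks the 24-month comparison of the arms.

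**What to change.** 1. Replace the between-arm t-test with ANCOVA of mHHS on arm with baseline mHHS as covariate, or with a mixed model over 12 and 24 months with baseline as covariate. Report the adjusted difference with its 95% confidence interval, and use robust standard errors to keep the provision for unequal variances. ANCOVA gives the same treatment effect whether the outcome is entered as change or as final score, so it also settles the mismatch with the endpoint wording. Do not move to an unadjusted change score.
2. In the last sentence of that paragraph, change 12 months to 24 months.
3. Add one sentence on how the 12- and 24-month results are read together. Hypothesis 1.4 reads as durability of the 12-month result, and no either-time rule is stated.
4. Make these changes in a dated amendment before any formal comparison of the arms, and keep the raw t-test as a sensitivity analysis.

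**Cost.** No new data or patients are needed. The statistical cost is one degree of freedom plus chance imbalance, about 0.5 point of power if r = 0. The procedural cost is the appearance of a late change in an unblinded trial, which the dated amendment and the retained t-test limit.

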In addition, subjects can subjectively withdraw from PT any time point if they feel that it is not working for them the way they would like. However, in order to standardize the amount of time that lapses between enrollment and potential cross-over, subjects wishing to transition to surgical treatment cannot do so until 6 weeks after initial enrollment (see figure 5 of the study schema). There are several reasons for this: First, we want subjects to have enough time to see the benefits of PT, as they may not be immediate. Second, if the decision to cross over is made prior to 6 weeks, the remaining time allows for scheduling of a follow-up appointment in a timely manner that does not delay appropriate patient care. Lastly, subjects are not required to continue under the PT protocol, they can stop at any point and not receive further PT or medically directed care until their follow-up. This scenario is no different than if a patient, in a non-study setting, self discontinued a recommended course of PT and sought surgical consultation elsewhere. The advantage here is that subjects will already be known to both the hospital system and surgeon, which allows for quicker consultation.

SURGERY

While randomization is a research procedure for this study, the surgery itself is not a research procedure. This surgery is standard of care for patients with symptomatic labral tears, and the PI regularly performs labral repair in patients not enrolled in research.

POSTOPERATIVE PROTOCOL

All procedures are performed on an outpatient basis. Patients are allowed flat-foot full weight bearing immediately postoperatively. Patients are instructed in gait training, keeping a level pelvis and avoiding any lurching of their pelvis during ambulation. Patients are kept weight bearing as tolerated with crutches for 6 weeks postoperatively for a labral repair. Patients are allowed full active range of motion as tolerated immediately with avoidance of deep squatting and impact loading exercises for 4 months postoperatively. This is considered standard practice.

V. BIOSTATISTICAL ANALYSIS

Hypothesis 1.1-1.4:

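### The plan does not say that the 12- and 24-month mHHS comparison is between the arms as randomised, although PT patients may cross to surgery from week 6 and surgical patients are removed after arthroscopy

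*Combined protocol and SAP*

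**What the plan says.** - **Endpoint.** Section III (Study Overview) makes change in mHHS at 12 and 24 months the primary outcome.
- **Analysis.** Section V, Hypothesis 1.1-1.4: "The mean outcomes scores of the mHHS between groups at 12 months will be compared using independent t-tests to assess for significant difference". The same section refers to each treatment group without defining membership. The 24-month comparison rests on hypothesis 1.4 and the primary outcome statement. No intention-to-treat, as-treated or per-protocol statement appears anywhere.
- **Crossover.** Section IV (Physical Therapy Visits) sends PT patients who fail the advancement criteria back to the surgeon for possible crossover. It adds that "subjects wishing to transition to surgical treatment cannot do so until 6 weeks after initial enrollment". Section VIII, item 1a, lets PT patients "cross over to the surgical treatment group at any time (following physical therapy) from initial enrollment if they wish to do so", and also makes official crossover wait for 6 weeks. The two timing statements should be reconciled, but both open crossover long before 12 months.
- **Removal.** Section III takes surgery-group patients out of the study if arthroscopy shows unexpected pathology, and lists this as an exclusion criterion.
- **Sample size.** The Power Analysis for Specific Aim 1 takes "a 10 point or greater difference on the mHHS as significant", one-sided 5% and 80% power, and concludes that "35 subjects are needed to demonstrate a statistically significant difference between the average mHHS of the conservative group and surgical group". The increase to 122 is explained by follow-up experience: "47 patients that had passed the 2-year follow-up mark, of which 5 patients were no longer in the study" (lost to follow-up or total hip arthroplasty), and 11 more had not returned surveys. It ends: "We enroll until reaching at least 35 subjects in each group". Crossover appears in this section only as a restriction on hypothesis 1.5, which is limited to PT patients who did not cross over.

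**The concern.** Crossover is a designed part of this trial, and one route into it is a poor response to PT. Which group a crossover belongs to at 12 and 24 months therefore decides what the primary comparison estimates. If crossovers stay in the PT arm, the comparison is randomised. If they are dropped or counted as surgical patients, the groups are selected partly on response and randomisation no longer protects the result. The trial is unblinded and the investigators review data continuously (Section VIII), so an unstated rule could be settled after crossovers and outcomes are known.

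The removal for unexpected pathology raises a related problem. Only operated patients can show such findings, so patients of the same kind stay in the PT arm and leave the surgical arm.

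The secondary issue is that the power statement is silent on crossover. If the 10 points is the difference between surgery and PT with nobody crossing, an as-randomised analysis targets something smaller.

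**Working it through.** **1. Does the text settle the groups?** Set side by side:

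| Leans towards as randomised | Leaves dropping or moving open |
|---|---|
| Section III randomises patients into two arms | Hypothesis 1.3 tests surgery plus PT against PT alone |
| Hypothesis 4.1 compares crossovers with patients originally randomised to surgery | Section VIII, item 1a, describes crossovers as joining the surgical group |
| The non-crossover limit is attached only to hypothesis 1.5 | Hypotheses 1.1-1.4 have no stated analysis population |

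The left column is the more natural reading, but nothing makes it a rule. Aim 4 analyses crossovers separately without saying where they count in Aim 1.

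**2. Reproducing 35 per arm.** The SD is not stated, so it must be back-solved. Normal approximation: SD = 10 × √(35/2) / (1.645 + 0.842) = 16.8. Noncentral t: SD = 16.66, standardised difference 0.600. The SD of about 16.7 used below is inferred, not a figure from the plan.

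**3. What the choice of population could do (illustrative).** Assume the worst-responding share c of the PT arm crosses over, and that response correlates r = 0.3 with the outcome. Neither value is in the documents. With φ(z) the normal density at the c quantile (0.1755 at 10%, 0.3477 at 30%):
- Retained PT patients shift by r × SD × φ / (1 − c): 0.3 × 16.66 × 0.1755 / 0.9 = 0.97; 0.3 × 16.66 × 0.3477 / 0.7 = 2.48.
- Crossovers shift by −r × SD × φ / c: −8.77 and −5.79. Pooled into the surgical group this moves its mean by −8.77 × 0.1/1.1 = −0.80 and −5.79 × 0.3/1.3 = −1.34.

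Surgery-minus-PT difference (negative favours PT):

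| Scenario | c | As randomised | Crossovers dropped | As treated |
|---|---|---|---|---|
| No true effect | 10% | 0 | −1.0 | −1.8 |
| No true effect | 30% | 0 | −2.5 | −3.8 |
| True 10 points, crossovers gain full benefit | 10% | 9.00 | 9.03 | 8.23 |
| True 10 points, crossovers gain full benefit | 30% | 7.00 | 7.52 | 6.18 |

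With no true effect, both alternatives favour PT. With a full-benefit 10-point effect, dropping crossovers gives a difference slightly larger than as randomised. In that scenario dropping falls below as randomised only when r exceeds 10c / [SD × φ / (1 − c)], about 0.31 at 10% and 0.36 at 30%. As treated does so at a lower r: 1.0 / (1.77/0.3) = 0.17 and 3.0 / (3.82/0.3) = 0.24.

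**4. Removal after arthroscopy (illustrative).** If a share u of the surgical arm is removed and would have scored δ below the rest, the arm mean rises by u × δ. With assumed δ = 10, u = 5% gives 0.5 points and u = 10% gives 1.0.

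**5. Power, only if the 10 points is before crossover.** As-randomised difference = 10 × (1 − b × c), where b is the share of surgical benefit that crossovers gain; noncentral t, one-sided 5%, SD 16.66, extra variance from mixing ignored.

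| Completers per arm | Full benefit: c = 10 / 20 / 30% | Half benefit: c = 10 / 20 / 30% |
|---|---|---|
| 35 (plan's floor) | 72 / 63 / 54% | 76 / 72 / 68% |
| 40 (122 × 31/47 = 80.5 in total) | 77 / 69 / 59% | 81 / 77 / 73% |
| 54 (122 × 42/47 = 109.0 in total; assumes only the 5 who left are missing at 12 months) | 87 / 80 / 70% | 90 / 87 / 84% |
| 61 (no loss) | 91 / 84 / 75% | 93 / 91 / 88% |

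With full benefit, 80% survives to about 7%, 20% and 25% crossover at 40, 54 and 61 per arm.

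**6. What 122 covers.** 70 / (31/47) = 106.1, so 107 enrolled would give 70 completers. The remaining 15 (122 − 107) are not explained. The allowance that is explained does not mention crossover.

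**The case against.** The strongest reply is that the plan already points to analysis as randomised. Patients are randomised into arms, crossovers have their own aim, hypothesis 4.1 keeps them apart from those first randomised to surgery, and limiting only hypothesis 1.5 to non-crossovers suggests that 1.1-1.4 carry no such limit. Joining the surgical group in Section VIII may describe care, not analysis. This is fair: a reader might infer that the sponsor intends to drop or move crossovers, and the documents do not show that. What remains is that a likely default is not a prespecified rule.

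A reader might also infer that any departure from as randomised favours PT. That does not hold for dropping crossovers: the direction depends on the true effect, on how much crossovers gain and on how strongly crossover tracks outcome, as step 3 shows. An as-treated analysis tends to favour PT, but that too requires crossover to track outcome closely enough.

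On unexpected pathology, the objection is that handling is already stated, because those patients are removed. That is correct. The problem there is the rule itself when applied to a randomised comparison, not missing detail.

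On power, the 10 points may be a threshold of importance for the as-randomised difference, in which case 80% stands. Larger completer numbers also absorb some crossover, and the 15 unexplained enrolments could serve any purpose.

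**Conclusion.** The point holds and should be fixed before analysis. Crossover linked to PT response opens at week 6, the primary comparison is at 12 and 24 months, and the plan does not tie that comparison to the assigned arm. As written it permits a non-randomised primary analysis, and it imposes a one-sided exclusion on the surgical arm after randomisation.

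The size is conditional. In the illustration, against a 10-point target, the choice of population moves the no-effect result by 1.0 to 3.8 points. With a true full-benefit effect it moves the result by less than 1 point relative to as randomised, and it may matter little at low crossover. These figures rest on a back-solved SD and assumed values of r and c.

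The power note is secondary. A reader might infer that the trial is underpowered; the documents do not support that, because they give no SD or crossover rate and do not say which difference the 10 points describes. The supportable statement is narrower: if the 10 points is before crossover and the analysis is as randomised, 80% at 35 per arm holds only without crossover that brings surgical benefit.

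**What to change.** In Section V:
- State that the 12- and 24-month between-arm mHHS comparisons use the arm assigned at randomisation. Crossovers stay in the PT arm. Surgical-arm patients with unexpected pathology stay in the surgical arm for this comparison, and are excluded only in a sensitivity analysis. Align the removal wording in Section III with this.
- Count the 35 per group by assigned arm.
- Label as-treated and crossover-excluded analyses secondary and observational.
- State the SD and whether the 10 points is before or after crossover. If before, restate the 80% as holding without crossover, and add a short table of power by crossover rate. The sponsor should be able to inform it with the crossover count among the 47 patients past two years by July 2018. If after, say so, and the 80% stands.

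The cost is protocol wording and at most one table, plus outcome surveys from surgical-arm patients who would otherwise be removed. The stated power may become less favourable. No new patients are needed and the crossover rule does not change.
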